9.1.6 Safety Considerations

- Surgical Complications: The stereotactic tumor biopsy and catheter implantation procedure carries a risk for cerebrospinal fluid leak, infection, hemorrhage, loss of neurologic function, non-neurologic complications and death. These risks depend primarily on the preoperative condition of the patient, the size and location of the tumor and associated diseases. The potential risk for the patient will be discussed in detail with the patient and family.
- Anesthesia: Patients undergoing general anesthesia may be subjected to associated risks including pneumothorax, pneumonia, airway injury, hypotension, myocardial infarction, stroke, hepatic and renal injury and death.

- **Poliomyelitis:** PVSRIPO has been tested in non-human primates according to the WHO standardized monkey neurovirulence tests. These tests revealed the absence of neuropathogenic properties, evident as failure to induce symptoms of poliomyelitis in non-human primates after intracerebral inoculation of virus. However, PVSRIPO is a replication-competent viral agent that, in principle, retains the potential to cause motor neuron damage. Possible complications include transient or permanent mono- or paraparesis, paralysis, and life-threatening respiratory insufficiency.
- **Virus Recombination and Mutation:** PVSRIPO retains the ability to alter its genome during replication upon administration to patients. Various mechanisms are known to lead to genetic adaptation, including spontaneous mutagenesis and recombination that may give rise to viral progeny with changed properties. Empirical studies in tissue culture and laboratory animals demonstrated that prolonged passaging in GBM cells does not select for genetic changes in viral progeny. However, the occurrence of such events cannot be categorically excluded in patients receiving intracerebral PVSRIPO. Genetic changes may cause an altered phenotype of PVSRIPO, including adaptation to improved virus replication in the normal CNS.
- **Long-Term Sequelae of Virus Injection:** PVSRIPO does not encode foreign genetic material; PVs are unable to insert viral genetic material in the host genome and PVs are incapable of inducing latent or chronic CNS infection. Therefore, PVSRIPO is unable to induce long-term expression of foreign polypeptides or long-term persistence. Thus, there are no long-term neurologic consequences to intracerebral PVSRIPO administration in study subjects. For these reasons, no specific measures to analyze the potential for persistence of virus replication in the CNS of long-term survivors are indicated.
- **Gastrointestinal Infection and Virus Excretion:** After oral uptake, PV replicates in the gastrointestinal tract and is excreted by infected individuals' stool. Gastrointestinal viral replication usually is asymptomatic, but may cause mild symptoms of gastrointestinal discomfort. Tests of PVSRIPO in non-human primates and in subjects from the phase I study suggest that excretion of PVSRIPO does not occur after intracerebral inoculation in immunized/boosted patients. This is based on thorough testing in patients in our Phase 1 clinical trial and much historical evidence from investigations in non-human primates.
- **Cerebral Edema and Increased Intracranial Pressure:** Cerebral edema may be secondary to the disease process itself, the surgical procedure, necrosis from previous radiation, or inflammation due to immune infiltration of the brain or destruction of tumor cells. Symptoms may include, but are not limited to, severe headache, confusion, lethargy, unresponsiveness, coma, or focal neurological deficits. Patients will be monitored throughout the course of the study and upon any signs or symptoms of cerebral edema, may have their steroid doses increased or receive treatment with an osmotic diuretic, or surgical decompression. Edema that fails to respond to aggressive therapy may lead to permanent neurological impairment. The probability of this risk can be predicted to some degree based upon tumor size, location, pre-operative neurological impairment, and post-operative course prior to virus administration.

Special Consideration: In the event that a patient demonstrates neurologic or radiographic signs suggestive of an inflammatory reaction secondary to the immune response triggered by PVSRIPO that requires a dose of dexamethasone above 4 mg a day after the first 2 weeks post PVSRIPO infusion, dexamethasone will not be increased any further. Instead, patients will be treated with bevacizumab 7.5 mg/kg IV every 3 weeks and neuroimaging (MRI) after 3 doses (every 9 weeks +/- 2 weeks) to assess if further treatment with bevacizumab is needed to control the cerebral inflammation. Bevacizumab will not be provided by the study. Every attempt should be made to discontinue dexamethasone. Once patients start bevacizumab, the follow-up visit schedule will be adjusted to coincide with the timing of the bevacizumab instead of the prior PVSRIPO infusion. Therefore, patients will return approximately every 9 weeks for an evaluation with MRI.

Per the packet insert for bevacizumab dated 12/2017, the safety and effectiveness of bevacizumab have not been established in the pediatric population ³³. Bevacizumab is currently not approved by the FDA for use in patients under the age of 18 years. “In published literature reports, cases of non-mandibular osteonecrosis have been observed in patients under the age of 18 years who have received Avastin ³³.” In initial Phase I and II clinical trials, four potential bevacizumab-associated safety signals were identified: hypertension, proteinuria, thromboembolic events, and hemorrhage. Additional completed Phase II and Phase III studies of bevacizumab in adults, as well as spontaneous reports have further defined the safety profile of this agent. Bevacizumab-associated adverse events identified in Phase III trials in adults include congestive heart failure (CHF) primarily in metastatic breast cancer, gastrointestinal perforations, wound-healing complications, and arterial thromboembolic events (ATEs). These and other safety signals are described in further detail in the bevacizumab package insert.

If there are adverse events or other circumstances prohibiting the use of bevacizumab, we will use corticosteroids or surgery, or other interventions deemed more appropriate for the patient by the treating physician, if needed, to treat the inflammatory reaction secondary to PVSRIPO.

- **Risk of Infection:** The intracerebral catheter placement and infusion may include the risk of infection. However, similar procedures including stereotactic biopsy and ventriculostomy placement are commonly used in the routine clinical care of patients with malignant brain tumors with a very low and acceptable rate of infection. In the most extreme situation, however, infection may lead to systemic bacterial/fungal sepsis and possibly death. The risk of infection will be minimized though by performing catheter implantations in the Operating Room. Patients will be monitored throughout the course of the study for any signs and symptoms of infection. If an active infection is suspected, patients will be cultured and treated with appropriate antibiotics.
- **Risk of Phlebotomy:** Drawing blood or inserting an intravenous catheter into an arm vein may result in bruising or swelling in the area of the insertion, bleeding at the site of the needle puncture, light headedness, fainting and very rarely, local infection, which may be severe. These risks are reduced by the fact that the blood will be drawn by a qualified physician, nurse or phlebotomist (a professional trained to draw blood).
- **Risks of MRIs:** Risks and/or discomforts associated with MRI scans include anxiety produced from being in a tight, enclosed space (claustrophobia). In addition, the machine operates using a large and powerful magnet, which attracts certain metals. Therefore, people with these metals in their bodies (specifically pacemakers, infusion pumps, metal aneurysm clips, metal prostheses, joints, rods or plates) will be excluded from the study. Patients will also be checked to make sure that they do not bring any metal objects into the MRI facility. Dental fillings are less affected by the magnetic fields generated and are therefore permitted. It will be asked that patients let the physicians conducting this study know of any metal in their bodies other than dental fillings. Depending upon the age of the patient, sedation for imaging may be needed. Risks of sedation include an allergic reaction, aspiration, and over-sedation. Use of an IV may cause bruising. Occasionally, an infection develops at the IV site.
- **Allergic Reactions to Contrast Agents:** During the MRI, patients will be given a contrast agent. The agent is given routinely to obtain enhanced MRI scans of the brain. The agent is administered through the vein and requires the placement of an IV catheter. The catheter placement is similar to drawing blood except that the catheter remains in the vein during the time the agent is actively delivered. The risks of a blood draw and insertion of a catheter are similar. There have been a few, rare cases of allergies to the agent used in MRI contrast enhanced scans. Patients with any known severe allergies (anaphylaxis) to contrast agents will be excluded from the study. Patients with mild allergies (i.e., rash only) will be pretreated

with Tylenol and Benadryl prior to injection of the contrast agent. In addition to the gadolinium (contrast agent) being given for MRI contrast, it will also be co-infused with the study drug to assess infusion distribution. It is not FDA approved for gadolinium to be administered in this way. The potential risks of intracerebral infusion of gadolinium contrast agents are not completely known but are believed to be small. Risks for infusion of gadolinium contrast agents intrathecally for procedures such as cisternography have been somewhat better studied, and were recently summarized by Selcuk et al (2009)³⁴. Encephalopathy, coma and seizures have been reported as side effects in case reports of accidental administration of large amounts of gadolinium contrast agents intrathecally in humans^{32,35}. When these contrast agents are used in appropriately low dose, however, the risk of intrathecal administration appears reasonably low. No neurological sequelae attributable to the procedure were detected in a series of 85 patients³⁴, in another series of 95 patients at a one year follow-up³⁶, or in any of 51 patients after over 4 years of mean follow-up in another study³⁷. Although these results cannot be extrapolated to the procedure proposed in the current research, they indicate that direct exposure of the brain to small amounts of gadolinium contrast agent is generally well tolerated.

A rare but serious adverse reaction has been observed in patients that received a gadolinium-based contrast material during MRI examinations, a reaction called nephrogenic systemic fibrosis (NSF). Patients with kidney disease are at increased risk of developing NSF. NSF may cause skin thickening, joint pain and/or swelling. In rare cases NSF can lead to lung and heart problems and cause death.

- Risks to Household Contacts of Study Subjects: Primate toxicology studies showed that intracerebral infusion of PVSRIPO does not lead to extraneuronal dissemination or replication and, hence, is not associated with virus shedding. Therefore, and because PV transmission occurs via the fecal-oral route, the likelihood of unintended exposure of patient household contacts is exceedingly low. If accidental exposure occurred, it would equal the risk of exposure to any type 1 Sabin vaccine virus or vaccine virus derivatives. Thus, in essence, exposure with PVSRIPO is equal to oral immunization with a safe version of type 1 Sabin. Since type 1 Sabin vaccine virus or vaccine virus derivatives have to be considered part of the human environment, exposure to PVSRIPO would not represent an added risk beyond the possibility for exposure that already exists.
- Unknown Risks: The overall risk classification of this research is unknown.

9.1.7 Missed Doses

This is not applicable, as the PVSRIPO is a single administration agent.

9.1.8 Concomitant Medications

9.1.8.1 Steroids

Corticosteroids should be used at the lowest dose to control symptoms of edema and mass effect, and discontinued, if possible. Use of corticosteroids should be recorded in the electronic database.

9.1.8.2 Anticonvulsants

Anticonvulsants drugs should be used or continued, if indicated. Use of such anticonvulsants should be recorded in the electronic database.

9.1.8.3 Growth Factors

Routine use of growth factors (i.e. G-CSF, GM-CSF, and erythropoietin) is not permitted. However, therapeutic use of G-CSF in patients with serious neutropenic conditions, such as sepsis, may be used at the investigator's discretion. Use of such growth factors should be recorded in the electronic database.

9.1.8.4 Anti-emetics

The use of anti-emetics will be at the investigator's discretion. Use of anti-emetics should be recorded in the electronic database.

9.1.8.5 Proton Pump Inhibitors

The use of proton pump inhibitors (PPI) (e.g. rabeprazole, omeprazole, pantoprazole, lansoprazole or esomeprazole) is allowed on this study.

9.1.8.6 Febrile Neutropenia

Febrile neutropenia should be managed according to the local institutional guidelines. Measures include laboratory testing, blood and urine cultures, and institution of broad spectrum antibiotics.

9.1.8.7 *Pneumocystis jiroveci* pneumonia (PJP) prophylaxis

The use of medication (i.e., Bactrim) for PJP prophylaxis in patients on chronic steroids is recommended, but is at the investigator's discretion.

9.1.8.8 Neurosurgical Procedures

If a neurosurgical procedure is required for a reason other than tumor progression (i.e. the onset of hydrocephalus), these procedures should be documented, but will not constitute criteria for declaring the patient "off therapy."

9.1.9 Study Drug Blinding

Not applicable

9.2 Rationale for Selection of Dose, Regimen, and Treatment Duration

Dose: The dose for this trial was selected based on IND-directed toxicity studies ²⁵ and on experience from an ongoing study in adults with recurrent WHO grade IV malignant glioma. Dose-range finding and toxicity studies in non-human primates documented the absence of viral encephalomyelitis, poliomyelitis and meningitis with intracerebral injection of PVSRIPO up to a dose of 5×10^9 TCID50 ²⁵. In the adult WHO grade IV malignant glioma study, 4 patients were dosed at the maximum dose of 1×10^{10} TCID50 without signs of viral encephalomyelitis, poliomyelitis or meningitis. Given that the brain size of the target population for this trial (children and young adults aged 4-21) is nearly identical to that of adults, and that the human brain is ~10-times the size of the primate species used in the IND-directed toxicity studies (*M. Fascicularis*), the dose of 5×10^7 TCID50 in this trial is 500-times below the maximum feasible safe dose in *M. Fascicularis* and 1000-times below the maximum dose in the adult WHO grade IV malignant glioma study. The proposed dose of 5×10^7 TCID50 corresponds to the dose selected for future studies based on the Phase I adult WHO grade IV malignant glioma study. If unacceptable toxicity that requires dose reduction occurs, according to Section 15.4.1, we may consider a PVSRIPO dose reduction to 3.3×10^6 TCID50.

Regimen and Treatment Duration: The treatment regimen for PVSRIPO is single intracerebral infusion, as in the ongoing adult WHO grade IV malignant glioma study.

9.3 Rationale for Correlative Studies

While tumor-selective PVSRIPO propagation is an important mediator of cytotoxicity, significant intra- and peritumoral inflammation likely ensues. This raises the possibility that an immunogenic response is being generated, certainly against the virus itself and with great likelihood against the tumor as well (Figure 2) ¹⁵. While the exact host immune response to PVSRIPO oncolysis is currently unknown (but is being investigated), host innate antiviral defenses are likely to trigger a broad immune effector cascade that needs to be examined in patients receiving PVSRIPO therapy. Blood will therefore be collected for immune function studies before and at periodic intervals following treatment with PVSRIPO.

9.4 Definition of Evaluable Subjects

Any patient who has undergone surgery, placement of the catheter, and any dose of PVSRIPO will be evaluable for both toxicity and efficacy of agent.

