8 OBJECTIVES AND ENDPOINTS

Table 1. Objectives and Endpoints

	Objective	Endpoint	Analysis
Primary	Confirm the safety of the selected dose of PVSRIPO when delivered intracerebrally by convection-enhanced delivery (CED) in children with recurrent Grade III or IV MG	Percentage of patients that experience unacceptable toxicity during the 14-day period post-PVSRIPO treatment. Proportion of patients who require low-dose bevacizumab or steroid treatment due to an inflammatory reaction secondary to an immune response to PVSRIPO treatment will be calculated.	See Section 15.4
Secondary	Estimate Overall Survival (OS) in children with recurrent WHO Grade III and IV malignant glioma treated with a single dose of PVSRIPO	Proportion of patients alive 2 years after PVSRIPO treatment	See Section 15.5

Exploratory	Describe changes visualized on imaging due to intratumoral inoculation of PVSRIPO	Description of imaging changes	See Section 15.6
Other Exploratory	Describe changes in tumor volume visualized on imaging after intratumoral inoculation of PVSRIPO	Change from baseline in tumor volume based on imaging	See Section 15.7
Other Exploratory	Assess immunologic responses in peripheral blood and in serum	Change from baseline in immune function	See Section 15.7
Other Exploratory	Identify genetic predictors of response or failure of response to treatment with PVSRIPO	Identification of genetic markers as predictors of response	See Section 15.7

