9.1.5 Definition of Unacceptable Toxicity

Toxicities will be graded according to the NCI CTCAE version 4 criteria. Any Grade 3 or any Grade 4 toxicity that is not reversible within 2 weeks, any life-threatening event deemed related to the study drug, or any treatment-related death will be considered unacceptable.

Any Grade 2 or higher autoimmune toxicities, particularly those affecting vital organs (e.g. cardiac, renal, CNS), will be considered an unacceptable toxicity, if it occurs within 2 weeks post-infusion. Grade 3 or higher surgical complications from insertion of the catheter are considered an unacceptable toxicity.

Exceptions to these unacceptable toxicities are as follows:

- Events associated with the biopsy procedure/catheter placement: Seizures or hemorrhages occurring during anesthesia or the biopsy/catheter insertion proper prior to administration of the agent if Grade 2 or lower.
- Seizures: Due to the nature of the disease under investigation in this protocol, patients may have pre-existing seizures or be susceptible to new seizures as a result of the underlying disease process. Although seizures may be defined as Grade 3 or 4 toxicities under NCI CTC, and will be reported as such in this protocol, seizures will not be considered an unacceptable toxicity if, in the opinion of the site Principal Investigator they have not increased in frequency or can be attributed to another recognized cause of increasing seizure frequency such as sub-therapeutic anti-convulsant levels or biopsy proven tumor progression.
- New or worsening neurologic deficits: Due to the nature of the disease under investigation in this protocol, patients may have an increase in pre-existing neurologic deficits or may develop new neurologic deficits as a result of tumor invasion. A new neurologic deficit, which resolves within 2 weeks after initiation of medical therapy, will not be considered an unacceptable toxicity. New neurological symptoms will not be an unacceptable toxicity if they can be ascribed to tumor progression (e.g. documented with histopathologic analyses of biopsy tissue), or they respond to treatment (e.g. oral steroids) within 2 weeks.

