12.1 Screening Examination

The screening examination will take place within 2 weeks before catheter placement. An informed consent must be signed by the patient and their legal guardian(s) before any study-specific screening procedure takes place. Within 6 months before receiving the PVSRIPO infusion, the patient should have received a PV booster, a serum test for LSQ and anti-tetanus toxoid IgG. The patient should also have whole blood drawn (up to 10 mL; red top tube(s)) for immunologic analysis and PV titer and an additional amount (up to 36 mL; yellow top ACD tube(s)) for other immunologic analysis during this time. Blood volumes drawn for immunologic analyses should not exceed 3 mL/kg in a 24 hour period or 7 mL/kg in an 8 week period, allowable per Duke policy. At the discretion of the investigator, blood volumes for immunologic analysis should be adjusted depending upon the weight of the child, in order to be consistent with Duke policy.

Pre-treatment evaluations within 2 weeks before catheter placement to determine eligibility and as a baseline will include the following, unless otherwise indicated:

- History and physical exam, including a full neurologic assessment and KPS or Lansky, within 2 weeks of catheter placement and within 5 days of PVSRIPO infusion
- Laboratory Evaluations:
 - CBC with differential
 - CMP
 - PT, aPTT
 - Beta-HCG, if appropriate (within 48 hours of catheter placement and PVSRIPO)
 - Anti-tetanus toxoid IgG (within 6 months of catheter placement and PVSRIPO)
 - LSQ (within 6 months of catheter placement and PVSRIPO)
 - Whole blood (up to 10 mL) for immunologic analysis and poliovirus titer
 - Whole blood (up to 36 mL, but not to exceed 3 mL/kg in a 24 hour period or 7 mL/kg in an 8-week period) for immunologic analysis (volumes drawn will be adjusted at the discretion of the Investigator, but will be based on the weight of the child to be consistent with Duke policy)
- Baseline MRI of the brain within 5 days of starting treatment

If a subject does not receive PVSRIPO, minimal records regarding the subject and the reason for screen failure will be retained in the study database.

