12.6.3 Replacement of Early Withdrawal(s)

Subjects that withdraw from the study prior to receiving PVSRIPO infusion, either voluntarily or due to ineligibility, will be considered non-evaluable; those subjects will be replaced.

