15.1 Analysis Sets

All patients who receive PVSRIPO treatment will be included in all safety and efficacy analyses.

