15.4.1 Overview of Study Design and Monitoring

Patients will be treated with PVSRIPO, then carefully monitored for safety for at least 1 year after treatment. Of particular interest will be the incidence of AEs that occur during the first 14 days after PVSRIPO treatment and the inflammatory events that occur during the first year after PVSRIPO treatment. The experience with PVSRIPO treatment of adult patients with recurrent WHO grade IV malignant glioma suggests that a patient remains at risk, during the first 12 months post-PVSRIPO treatment, of demonstrating neurologic or radiographic signs suggestive of an inflammatory reaction secondary to the immune response triggered by PVSRIPO that requires a dose of dexamethasone above 4 mg a day. As described in Section 9.1.6, such patients will be treated with bevacizumab 7.5 mg/kg IV every 3 weeks if possible, or alternatively corticosteroids or surgery.

Two sets of safety monitoring guidelines are proposed, with one focused on acute toxicity (i.e. occurring during the first 14 days after PVSRIPO administration), and one focused on long-term issues.

Acute Toxicity Monitoring Guidelines: Monitoring rules based upon the occurrence of an unacceptable toxicity, as defined in Section 9.1.5, during the first 14 days after PVSRIPO administration are shown below in **Table 4**.

If the number of patients with an unacceptable toxicity surpasses the noted thresholds, accrual will be suspended. Data will be carefully reviewed to determine if accrual should be terminated, continued without modification, or continued with appropriate modification (e.g. PVSRIPO dose reduction).

Table 4. Acute Toxicity Monitoring Rules.

# of Patients Accrued	Accrual Suspension Threshold
0 – 6	≥2 patients with unacceptable toxicity
7-9	≥3 patients with unacceptable toxicity
10-12	≥4 patients with unacceptable toxicity

The probability of study suspension and the expected number of treated patients before study suspension is tabulated below in **Table 5** as a function of the true underlying probability of an unacceptable toxicity.

Table 5. Probability of study suspension.

True Underlying Probability of a Unacceptable Toxicity within 14 days of PVSRIPO administration	Probability of Accrual Suspension	Expected Number of Patients to be Accrued
0.05	0.030	11.8
0.10	0.124	11.1
0.15	0.262	10.2
0.20	0.411	9.2
0.25	0.560	8.1
0.30	0.681	7.2
0.35	0.792	6.2
0.40	0.873	5.4

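### Grade 3 or higher catheter complications count as unacceptable toxicity in 9.1.5, but the primary percentage and Table 4 as written miss those that prevent or precede infusion

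*Combined protocol and SAP*

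**What the plan says.** **What counts as an event.** Section 9.1.5 states: "Grade 3 or higher surgical complications from insertion of the catheter are considered an unacceptable toxicity". It does not require that PVSRIPO was given. The first exception in that section excuses seizures and hemorrhages during anesthesia or the biopsy/catheter step, before the agent is given, only when they are Grade 2 or lower.

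**Who is counted.** Section 9.4: "Any patient who has undergone surgery, placement of the catheter, and any dose of PVSRIPO will be evaluable for both toxicity and efficacy". Section 15.1: "All patients who receive PVSRIPO treatment will be included in all safety and efficacy analyses".

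**When they are counted.** Table 1 gives the primary endpoint as "Percentage of patients that experience unacceptable toxicity during the 14-day period post-PVSRIPO treatment", and 15.4.2 repeats it. Section 15.4.1 introduces Table 4 as "Monitoring rules based upon the occurrence of an unacceptable toxicity, as defined in Section 9.1.5, during the first 14 days after PVSRIPO administration". Table 5 is labeled with the same window. Section 9.1.2 lets the infusion start the day after catheter placement.

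**What happens to patients who are not infused.** Section 12.6.3 says that those who withdraw before infusion, "either voluntarily or due to ineligibility, will be considered non-evaluable; those subjects will be replaced". Section 12.1 adds: "If a subject does not receive PVSRIPO, minimal records regarding the subject and the reason for screen failure will be retained". Sections 5.5 and 15.9 cap the study at 12 treated patients.

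**Where such events do appear.** Section 13.1 requires AE recording from the first study-related procedure. Section 13.2.1 sends every SAE to the sponsor within 24 hours, related or not. Section 15.3 reports the number catheterized and the number then infused. Section 15.4.2 summarizes AEs from catheter placement onward.

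**The concern.** The primary objective is the safety of the dose as delivered by convection-enhanced delivery, so the operation is part of what is being judged, and 9.1.5 treats it that way. The population and the window are both set by receipt of PVSRIPO, which comes after the operation. Whether a patient enters the count can therefore depend on how the operation went: a complication bad enough to stop the infusion takes the patient out of both numerator and denominator.

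Two results are at stake. The unacceptable-toxicity percentage would be too low for the delivered treatment. The Table 4 rule, which suspends accrual in a pediatric trial, would not respond to these events. Two consecutive patients with a severe catheter hemorrhage and no infusion would add 0 to a threshold of 2.

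**Working it through.** **1. The passages side by side.**

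| Event | Unacceptable under 9.1.5? | In the 9.4/15.1 population? | In the 14-day window? |
|---|---|---|---|
| Grade 3+ catheter complication after infusion starts | Yes | Yes | Yes |
| Grade 3+ catheter complication before infusion, patient infused later | Yes | Yes | No, read literally |
| Grade 3+ catheter complication, patient never infused | Yes | No | No window exists |

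The Grade 2 exception matters here. Exempting low-grade events before administration is needed only if events before administration can count. The definition therefore reaches Grade 3+ events that the counting rules leave out.

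**2. Reproducing Table 5.** Inputs are the Table 4 thresholds (2 events for up to 6 patients, 3 for 7–9, 4 for 10–12) and N = 12. An exact binomial recursion that checks the rule after every patient gives:

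| True rate p | Stated suspension probability | Recomputed | Stated expected N | Recomputed |
|---|---|---|---|---|
| 0.05 | 0.030 | 0.035 | 11.8 | 11.75 |
| 0.10 | 0.124 | 0.128 | 11.1 | 11.11 |
| 0.15 | 0.262 | 0.259 | 10.2 | 10.21 |
| 0.20 | 0.411 | 0.408 | 9.2 | 9.19 |
| 0.40 | 0.873 | 0.872 | 5.4 | 5.45 |

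The other rows agree as closely. Table 5 is correctly calculated for the rate after infusion. It has no term for patients who have a catheter placed but are not infused.

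**3. Chance that at least one event is omitted.** Let q be the probability of an unacceptable complication that prevents infusion. The documents do not give it, so q = 2%, 5% and 10% are assumptions. The formula is 1 − (1 − q)^n.

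| q | n = 12 | n = 7 |
|---|---|---|
| 2% | 1 − 0.98^12 = 0.215 | 1 − 0.98^7 = 0.132 |
| 5% | 1 − 0.95^12 = 0.460 | 1 − 0.95^7 = 0.302 |
| 10% | 1 − 0.90^12 = 0.718 | 1 − 0.90^7 = 0.522 |

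The n = 7 column is the 12-patient cap less the 5 patients whom 5.5 reports as already treated.

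**4. Effect on suspension.** Suppose 20% of patients who start the procedure have an unacceptable event, and q of that prevents infusion. Among infused patients the rate is (0.20 − q)/(1 − q). For q = 5% this is 0.15/0.95 = 0.158. Plain subtraction gives 0.15 and a suspension probability of 0.26, but it keeps the wrong denominator.

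| q | Rate among infused | Suspension, all starters counted | Suspension, as written |
|---|---|---|---|
| 2% | 0.18/0.98 = 0.184 | 0.41 | 0.36 |
| 5% | 0.15/0.95 = 0.158 | 0.41 | 0.28 |
| 10% | 0.10/0.90 = 0.111 | 0.41 | 0.15 |

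The first suspension column follows 12 patients who start the procedure; the second follows 12 infused patients.

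**5. Effect on the percentage.** With 1 event in 12 infused patients the estimate is 8.3%. One omitted patient makes it 2/13 = 15.4%; two make it 3/14 = 21.4%.

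**The case against.** **The events are not lost.** A reader might infer that a child harmed by the catheter disappears from the trial, or survives in the record only as a screen failure with minimal data. The documents do not support that. AE recording, 24-hour SAE reporting, the catheter and infusion counts and the AE summary from catheter placement all reach these patients, and under 13.7 the external DSMB-Plus can recommend stopping. The loss is confined to the primary percentage and the Table 4 count. A descriptive table feeds neither.

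**Replacement is not stated for this case.** Section 12.6.3 names voluntary withdrawal and ineligibility; a surgical injury is neither. The minimal-records sentence sits under screening, so applying it to an operated patient is a reading. Both points stand. The cap on treated patients nevertheless has the same effect as replacement, because an uninfused patient uses no slot.

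**The text may be ambiguous rather than exclusionary.** Section 15.1 says who is included, not who is excluded. Section 9.4 concerns toxicity of the agent. Table 4 labels its rows by patients accrued. Section 9.1.2 keeps the day-0 label when infusion slips by a day. These support an intention to count, but none changes a window worded as following PVSRIPO administration. They show that the passages need reconciling.

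**An infused-only set suits a dose-safety question.** It does, and it should be reported. It does not fit a definition of unacceptable toxicity that includes catheter insertion.

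**The remaining effect is smaller.** Section 5.5 reports no dose-limiting toxicities in the first five treated patients. If that also means no Table 4 events among them, which is an assumption, the contrast for the remaining seven slots at a 20% rate and q = 5% is 0.046 against 0.022. The 0.41 and 0.28 figures describe the design stage only.

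**Conclusion.** The inconsistency is real and needs correcting. As written, a Grade 3 or higher catheter complication that prevents infusion, or precedes it in a patient infused later, meets the 9.1.5 definition but enters neither the primary percentage nor the Table 4 count.

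The structural conclusion rests on the wording alone. Its size rests on an assumed q. For q of 2% to 10%, the chance of at least one omission is 22% to 72% over 12 procedures, or 13% to 52% over the seven slots left. Design-stage suspension probability at a 20% total rate falls from 0.41 to between 0.36 and 0.15, and to about 0.28 at q = 5%. At this sample size one omitted patient can move the percentage by about 7 points (8.3% to 15.4%). Table 5 is not miscalculated, and the documents do not show that any such event has occurred.

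**What to change.** - Count 9.1.5 surgical events from the start of the protocol biopsy/catheter procedure, in every patient who starts it, in both the primary percentage and Table 4, whether or not PVSRIPO follows.
- Align 9.4, 12.6.3, 15.1, Table 1, 15.4.1 and 15.4.2 with that population and starting point. Replacement to reach 12 treated patients can remain, provided replaced patients who were operated on stay in the safety count.
- State in 12.1 that the screen-failure and minimal-records provision does not apply to operated patients, and collect their AEs for 14 days.
- Relabel Table 5 to the new denominator. Say how Table 4 applies if more than 12 patients start the procedure; at q = 5% about 12/0.95 = 12.6 starts are expected for 12 infusions.
- Report the infused-only rate alongside, and keep the infused set for OS.

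The cost is rewording, 14-day AE data on a few more patients and possibly a less favorable toxicity percentage.
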